2.5 Participant identification / Screening

The intervention will be delivered by ambulance staff attending patients sustaining cardiac arrest. 'Ambulance staff' refers to a range of staff grades normally sent to treat cardiac arrest and including paramedics, technicians, associate ambulance practitioners, emergency care assistants, ambulance nurses, specialist paramedics, and doctors. In this protocol the term 'staff member' will be used to denote any of these grades. Resuscitation is commenced, if appropriate, according to Joint Royal College Ambulance Liaison Committee (JRCALC) guidelines.

Patients receiving initial shocks from non-ambulance service defibrillators (e.g. public access defibrillators) may be included in the study. A patient may be eligible, but not recruited, if the incident was attended by a POSED vehicle carrying its allocated defibrillator, but shocks were delivered by an ambulance service non-POSED defibrillator.

Recruitment rates will be monitored via ambulance service call and clinical record databases. Screening logs will be kept listing potentially eligible patients who are not recruited.

2.6 Site Staff Information

Study-specific information will be delivered to ambulance staff providing the study intervention including:

[figure not shown]
- Background and rationale for study
- Ethical issues and consent
- Overview of GCP principles and specific study-related elements
- Study design
- Data collection and documentation

[figure not shown]
2.7 Informed consent

Based on the rationale in section 1.5, permission to take deferred consent for continuation in the study will be sought from the ethics committee. Conducting emergency research requires the building and maintenance of public trust and a sensitive approach to information sharing.[40, 26] Developing public awareness of a study has been found to reassure those recruiting patients into deferred consent studies of the acceptability of this approach.[41] Decisions regarding the level and timing of the receipt of information will vary according to a person's relationship to the study. For example, the relatives of a non-surviving participant may have different informational needs and capacity to process information from those of a surviving participant.

The diagram below outlines the general approach to the communication of study information.

Figure 3: Strategies for informing participants/relatives/professional consultee

2.7.1 General information regarding the study

We will make available general information about the study on the University website. In addition, general information regarding the study will be made available on the Ambulance service website, public newsletters and through discussion at public meetings. All of these channels will include contact details for further information. In this way members of the public may receive basic information and then choose whether and when to seek further details.

2.7.2 Informing survivors of their inclusion

Survival status of study participants will be tracked via the hospital research teams. Sensitive consideration of the most appropriate time to approach survivors must balance the legal duty to inform with the vulnerable emotional state of survivors and relatives in the early stages of their post cardiac-arrest journey. Our experience with PARAMEDIC2 and discussions with our patient and public advisory panel indicate that the earliest time for this approach is after the initial emergency has passed. This is usually once the patient has left a critical care area (such as the Intensive Care Unit (ICU), High Dependency Unit (HDU) or Coronary Care Unit (CCU) and been moved to a ward. This also allows time for the research team to be made aware of the enrolment, track their location and verify their survival status. A research paramedic will attempt to contact the ward nurse

responsible for the patient's care. This is the healthcare professional who may most quickly develop and maintain rapport with the patient and their family as well as having an ongoing awareness of the patient's mental capacity. Together they will negotiate the most appropriate and earliest visiting time. The research paramedic will meet with patient and, ideally, their family and will first assess the patient's mental capacity. If they have capacity to consent the research paramedic will provide a patient information sheet, discuss the study and inform them of their enrolment. We know from previous experience with the PARAMEDIC2 trial that patients and their families value this contact with paramedics who can also answer any questions regarding the prehospital phase of their care.

Patients shall then be given sufficient time to read through the information, discuss with others and have any questions answered before potentially giving consent.

Patients may decide that they do not wish to discuss the study or to participate. They are free to withdraw from the study at any time without giving reasons and without prejudice to any further treatment. In any of these situations, the patient's decision shall be respected and recorded, and contact details provided should they wish to obtain further information about the study.

In order to keep their care team informed, we will write to the GPs of all recruited patients.

2.7.3 Patients who lack capacity

Where patients lack capacity, we will attempt to contact a personal consultee to ascertain the patient's wishes. Should no personal consultee be available, a nominated consultee shall be approached. An appropriate consultee would be a medical practitioner who is not connected with the study. A similar process to that outlined above shall be followed with identification of a suitable consultee to be discussed with the hospital nursing team. The consultee shall be notified of the patient's enrolment and provided information about the study via the consultee information sheet (CIS). Rather than providing consent, a consultee will be asked for their opinion on whether the patient would have been likely to consent for follow up. If they consider that the patient would have no objection, the consultee will be asked to sign a consultee declaration form.

Prior to conducting follow-up we will attempt to ascertain whether the patient has regained capacity through consultation with the patient's nurse. If the patient is thought to have regained capacity, a meeting will be arranged as above, information provided to the patient and their consent for follow up sought.

2.7.4 Patients who have capacity but require additional support

Interpreters will be sought for patients who do not speak English. If patients are able to give informed consent but are not able to sign the form, we will ask a witness to sign the consent form to confirm that the patient has given verbal consent for follow-up.

2.7.5 Patients who have already been discharged from hospital

In the event that a patient is discharged before we have made contact with them, Research Paramedics will send a letter to them at their discharge address informing them of the study and inviting their continued involvement in the study. Prior to sending the letter confirmation will be sought that the patient has not died by consulting two information sources, the patient's GP and the NHS Summary Care Record.

2.7.6 Obtaining consent

Since the study intervention will already have been given at this point, consent will be sought for follow-up i.e. assessment of their neurological status at 30 days and at hospital discharge. Ideally consent will be sought from the patient, or an opinion from their consultee, on the hospital ward. In exceptional cases, when contact has not been made in hospital, if the patient or their consultee responds to the invitation letter a home visit will be arranged during which consent will be sought. Research paramedics shall manage the consent process. The PI shall ensure that appropriate training is provided to ensure that they are competent to fulfil this delegated responsibility.

The consent form will explicitly list all of the activities and data sources for which consent is sought, allowing the option to choose those for which consent is granted. Data already collected prior to the meeting will be retained unless explicit consent for its use is denied.

2.7.7 Non-survivors

Sadly, most victims of out-of-hospital cardiac arrest do not survive. At the time of death, the study intervention will already have been delivered and no follow up will be conducted and so the provision of consent is not necessary. The aim of any communication with the relatives of non-survivors would therefore be to demonstrate openness and transparency about study participation. This may reduce mitigate any potential future harm that could result from discovering at a later date that their relative had been enrolled in a study without their knowledge. We know from our experience with PARAMEDIC2 that this situation, on the few occasions that it occurred, was extremely distressing for relatives.

We have consulted with our local PPI advisory panel, the University Hospitals Birmingham NHS Foundation Trust PPI (Clinical Research Ambassador Group) group, international researchers and a bereavement lead and patient representative from a local ED regarding the acceptability of informing relatives at this vulnerable time. We have carefully considered their differing views and, on balance, have decided that the best approach would be to inform relatives of the enrolment via a sensitively worded letter. Our advisors felt that the principles of openness and transparency were most important and that by actively engaging with relatives this would preclude possible chance discovery in future which could provoke additional distress and set them back in the bereavement process. Identification of the most appropriate timing of receipt of a letter, again, divided opinion. We have decided that, in common with international practices and the bereavement services of a local hospital, around 4-6 weeks post death would be the optimal time. This would, it is felt, avoid intrusion on the immediate grieving period.

Our PPI advisors have helped us to create a letter of condolence that minimises the burden of information whilst offering support and further information if desired. This approach empowers people to decide whether and when to seek information.

2.8 Randomisation

2.8.1 Randomisation

Due to the time-critical nature of cardiac arrest, delay to shock delivery must be minimised. Any method of individual patient randomisation would necessarily incur a delay as the shock energy would need to be adjusted on the defibrillator. For this reason, randomisation will be on a cluster basis, the unit of randomisation being the defibrillator. Defibrillators are allocated to specific vehicles (ambulances or rapid response cars) and are not usually moved between vehicles as they are paired with the on-board electronic patient record tablet device. *The trial initially defined a cluster as a defibrillator, which as noted above, according to ambulance protocols, should remain co-located with a specific ambulance vehicle. During the conduct of the trial, it became evident that, on occasion, defibrillators became separated from their associated ambulance vehicles. As the Ambulance Service tracks vehicles rather than defibrillators it was only possible to track patients where the vehicle and defibrillator remained together. After careful consideration by the Sponsor, with input from the patient and public advisory group and approval from the Research Ethics Committee, the definition of a cluster was clarified as a defibrillator carried by its associated ambulance vehicle.* To minimise the risk of movement, defibrillator bags will be marked with the callsign of their allocated vehicle and display stickers reminding staff not to move them.

Defibrillators *on their associated ambulance vehicles* will be allocated to one of the three treatment groups in a 1: 1: 1 ratio. The randomisation schedule will be prepared by the study statistician and defibrillators shall be allocated to a treatment arm in a 1: 1: 1 ratio using simple randomisation. The statistician shall ensure that the sequence is not predictable based on vehicle type.

The experimental protocol ends after three shocks. In the event of a change of defibrillator during a patient care episode, normal trust policy will apply regarding shock energy escalation (i.e. second and subsequent shocks to be delivered at 200J).

At the point of device charging, staff will know which treatment they are delivering and so will not be blinded. Possible performance bias will be assessed by monitoring variables such as numbers of patients conveyed to hospital and not conveyed in each of the treatment arms.

Due to the unpredictable nature of out-of-hospital cardiac arrest it is not possible to sequentially allocate ambulances, and hence defibrillators, to events.

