2. STUDY DESIGN

2.1 Study summary and flow diagram

POSED is a stand-alone open-label feasibility study. A single-centre, cluster-randomised multi-arm study will be performed to assess feasibility measures that would inform the design of a large-scale trial. This single-centred study will be hosted by South Central Ambulance Service, an NHS ambulance service in the south of England.

The population of interest is patients sustaining out-of-hospital cardiac arrest who, on assessment by an ambulance crew, display a shockable cardiac rhythm (VF or pulseless ventricular tachycardia (VT)). This may be the initial or subsequent rhythm.

Defibrillators will be randomised to deliver one of three shock strategies:

Group	First shock	Second shock	Subsequent shocks	Strategy
1	120	150	200	Escalating
2	150	200	200	Escalating
3	200	200	200	Fixed

The comparator groups have been selected as they represent current UK practice. Group 1 delivers shock energies according to manufacturer's current guidance. Group 2 delivers shock energies according to current practice at the study site, but this is anomalous to the other NHS ambulance services. Although none of the UK ambulance services currently employs the group 3 energies, equivalent energy settings, i.e. high-high-high, are employed using BTE waveform in a number of NHS ambulance services. Group 3 is representative of current practice in these ambulance services.

In preparation for this study, a small scoping exercise of paramedics was conducted within the proposed study site. The scoping exercise found that 70% of paramedics felt that the first shock should be >120J whilst 95% felt that an escalating regime should be used. Whilst holding opinions on shock strategy, the exercise revealed that 30% of paramedics did not know what energies their defibrillators were programmed to deliver. When asked about the acceptability of randomising the intervention, 95% indicated that they would be willing to take part in a study comparing fixed and escalating shock levels.

Each shock takes a fraction of a second to be delivered by the defibrillator to the patient's heart. Patients may require one or many shocks during the pre-hospital phase. The resuscitation attempt may last from 20 min to approximately 60 minutes depending on journey time to hospital. Study treatment ceases on the handover of care to the hospital team who will continue with their normal care from this point.

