2.9.2 Compliance/contamination

It will be important to monitor adherence to treatment allocation. Treatment *delivery* will be compared to treatment *allocation*. Should the energy delivery differ from that which was allocated, this shall be deemed non-compliance and will be documented. Treatment delivery will be monitored by retrieving the defibrillator data download.

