6.2.3.3 Secondary outcome analysis

The secondary outcomes that will be assessed are:

- Treatment adherence rate. This will be assessed in terms of how many patients received the allocated first shock energy and, where more than one shock was delivered, how many received the correct subsequent shock energies.
- Data completeness of clinical outcomes below:
 - Neurologically intact survival at 30 days and hospital discharge (mRS score)
 - Return Of Organised Rhythm (ROOR) 2 min post shock

- Resulting rhythm (VF/pVT/PEA/asystole) 2 min post shock
- Re-arrest rate (re-fibrillation)
- Survived event (return of spontaneous circulation (ROSC) at hospital handover)
- Survived to hospital discharge and 30 days

These will be reported in terms of the proportion of patients for whom each of these outcomes was collected.

- Data completeness of process outcomes below:
 - Quality of CPR (chest compression rate, chest compression depth, chest compression fraction, pre-shock pause, post-shock pause)
 - Number of shocks
 - Advanced airway applied (% advanced airway applied and % supraglottic airway or endotracheal tube)
 - Intravenous medicines administered (% cases where medicines administered and % adrenaline, amiodarone)
 - Transported to hospital (% transported)
- Issues identified by ambulance staff and suggestions for study optimisation. These will be reported in terms of the topics identified, with example anonymised quotes, from the thematic analysis of the focus group data.
- Acceptability of approach to informing relatives of non-survivors. We will monitor the number and nature of enquiries received by the Ambulance Service, the time taken to identify next of kin, the sources consulted to verify next of kin details and the concordance/discordance between different sources.

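### After a change of defibrillator between the first and second shock, the protocol directs an energy that its own compliance rule scores as non-compliance in Group 1 only; shock numbering after a public-access shock is also not stated

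*Protocol*

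**What the plan says.** The table in Protocol section 2.1 sets the energies (J) for first, second and subsequent shocks: Group 1 "120 150 200 Escalating", Group 2 "150 200 200 Escalating", Group 3 "200 200 200 Fixed".

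Section 2.8.1 covers a change of defibrillator during a care episode: "normal trust policy will apply regarding shock energy escalation (i.e. second and subsequent shocks to be delivered at 200J". The rule does not depend on the arm. Section 2.8.2 says that the allocation fixes the energies of the first three shocks and makes no exception for a device change.

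Section 2.9.2 defines the departure: "Should the energy delivery differ from that which was allocated, this shall be deemed non-compliance and will be documented". Section 6.2.3.3 defines the adherence outcome: "This will be assessed in terms of how many patients received the allocated first shock energy", and for patients with more than one shock, how many received the *correct* later energies. It does not define *correct* after a device change. Section 6.4 defines a protocol-compliant population by receipt of the intervention that the protocol requires.

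On patients already shocked before the ambulance device is used, section 2.5 says: "Patients receiving initial shocks from non-ambulance service defibrillators (e.g. public access defibrillators) may be included in the study".

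**The concern.** Two rules in the protocol give opposite answers for one patient. Section 2.8.1 tells the crew what to deliver after a device change, and 2.9.2 then records that delivery as non-compliance if the patient is in Group 1. The same conduct in Group 2 or 3 is recorded as compliance.

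Adherence to allocation is the first-listed secondary objective. Section 2.1 reports that 70% of paramedics in a scoping exercise favoured a first shock above 120 J. A Group 1 shortfall that comes from the scoring rule could therefore be misread as reluctance to use the lowest-starting arm. Membership of the protocol-compliant population is also open for these patients.

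The case is foreseeable. Section 2.8.1 writes a rule for it, and 2.5 expects ambulance defibrillators outside the study to be used at some incidents.

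The public-access question is related but of a different kind. Section 6.2.3.3 scores the first shock without saying whether that is the patient's first or the study device's first. No section says whether moving from a public-access device to the study device is a change of defibrillator under 2.8.1.

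**Working it through.** There is no stated figure to reproduce, so the check compares allocated with delivered energy under each rule.

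**Inputs.** Allocated sequences from 2.1: 120/150/200, 150/200/200 and 200/200/200 J. Energy after a change, from 2.8.1: 200 J for second and later shocks. Scoring rule from 2.9.2: any difference is non-compliance. Planned size from 6.1: 30 per arm.

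**Step 1. Change from the allocated device to another.**

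| Change falls | Group | Allocated | Delivered under 2.8.1 | Scored under 2.9.2 |
|---|---|---|---|---|
| after shock 1 | 1 | 120-150-200 | 120-200-200 | mismatch at shock 2 |
| after shock 1 | 2 | 150-200-200 | 150-200-200 | match |
| after shock 1 | 3 | 200-200-200 | 200-200-200 | match |
| after shock 2 | 1, 2, 3 | as allocated | as allocated | match |

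The conflict is confined to Group 1, to the second shock, and to a change between shocks 1 and 2. First-shock adherence is untouched.

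**Step 2. Size.** The protocol gives no frequency of device changes. Let q be the share of all Group 1 patients whose device changes between shocks 1 and 2 and who then receive a second shock. Assume 30 patients per arm and full adherence otherwise.

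- Patients scored non-compliant by rule alone = 30 × q.
- Group 1 adherence = 1 − q; Groups 2 and 3 stay at 100%.
- Overall adherence = 1 − q/3.

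| q (assumed) | Group 1 patients affected | Group 1 adherence | Overall |
|---|---|---|---|
| 2% | 0.6 | 98% | 99.3% |
| 5% | 1.5 | 95% | 98.3% |
| 10% | 3 | 90% | 96.7% |
| 20% | 6 | 80% | 93.3% |

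Section 6.2.3.3 scores later shocks among patients with more than one shock. On that denominator the proportion affected would be at least as high as q, but the share who need a second shock is not given.

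**Step 3. One earlier public-access shock.** Two questions are open: whether the device runs its own sequence or the 200 J rule applies, and whether shocks are counted per device or per patient.

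| Reading | Group 1 | Group 2 | Group 3 |
|---|---|---|---|
| (a) own sequence, counted per device | compliant | compliant | compliant |
| (b) own sequence, counted per patient | non-compliant | non-compliant | compliant |
| (c) 200 J rule, counted per device | non-compliant | non-compliant | compliant |
| (d) 200 J rule, counted per patient | non-compliant | compliant | compliant |

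Three of the four readings give adherence that differs by arm. Reading (a) does not.

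**The case against.** The strongest reply is that 2.9.2 measures what patients received, not whether crews obeyed. A Group 1 patient given 200 J at shock 2 did not receive the allocated strategy, and if that arm is more exposed to device changes, a main trial needs to know. This stands in part. It is a reason to report such shocks, but not to count them with departures that the protocol did not direct.

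A second reply is that *correct* in 6.2.3.3 and the wording of 6.4 can be read as accepting a shock that 2.8.1 itself directs. That reading is available, but 2.9.2 says the opposite, so the sections disagree. Section 2.5 may also take some patients out, because it treats those shocked by a non-study ambulance defibrillator as possibly eligible but not recruited. It does not clearly cover a patient whose first shock came from the allocated device.

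A reader might infer more than the text supports:

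- **That 2.5 and 2.8.1 contradict each other on public-access patients.** They need not. Section 2.1 attaches the sequence to the defibrillator, which supports reading (a), under which nothing conflicts. What is missing is a numbering convention.
- **That only Group 1 is ever affected.** This holds for a change from the allocated device, not for public-access patients, where Group 2 is also affected under readings (b) and (c).
- **That Group 2 adheres without effort and a pooled figure would hide problems elsewhere.** Section 2.1 does say "Group 2 delivers shock energies according to current practice at the study site". However, randomising the device is meant to avoid adjusting energy at the scene in any arm, and nowhere does the protocol say that adherence will be pooled.
- **That adherence decides whether a main trial proceeds.** The protocol sets no adherence threshold.
- **That a rate among patients needing a second shock can be applied to all 30 in the arm.** This overstates the count unless all 30 need one.

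**Conclusion.** The point holds in a narrow form. Sections 2.1, 2.8.1, 2.8.2 and 2.9.2 conflict on the second shock in Group 1 when the defibrillator changes between shocks 1 and 2, and 6.2.3.3 and 6.4 leave the scoring of those patients inconsistent. That part follows directly from the text and needs no assumption.

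The size does need one: about 0.6 to 6 of 30 Group 1 patients for an assumed 2% to 20%. The numbering of shocks after a public-access shock is a separate gap, harmless on one reading and arm-dependent on three.

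What is affected is a descriptive secondary outcome and the protocol-compliant population. The primary count of eligible and recruited patients is not affected. The point merits correction because the present wording mixes protocol-directed switches with true non-adherence in one arm.

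**What to change.** Reconcile sections 2.1, 2.5, 2.8.1, 2.8.2, 2.9.2, 6.2.3.3 and 6.4 on what applies after a change of defibrillator and after a public-access shock. Which energy that should be is not a matter for this review.

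For the analysis:

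- Number shocks from the first one delivered by the allocated defibrillator, and assess adherence on shocks from that device.
- Report shocks after a device change as protocol-directed switches, by arm and shock number, and not as non-compliance.
- State in 6.4 whether a patient with such a switch belongs to the protocol-compliant population.
- Show patients with an earlier public-access shock separately.

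With shocks after a change left out of the adherence denominator, non-compliance caused by the device-change rule alone is 0 in all three arms.

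The cost is wording, a little more tabulation and a smaller denominator for later-shock adherence. The data come from the defibrillator downloads already planned in 2.9.2.

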6.2.3.2 Primary outcome analysis

The primary objective of this study is to establish whether it is feasible to conduct a large-scale definitive study. We will report the proportion of eligible patients who receive the randomised intervention.

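### Crews can know a vehicle's arm before they reach later patients, and a primary proportion not split by arm cannot show whether recruitment or choice of device depended on it

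*Protocol*

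**What the plan says.** **Allocation.** Protocol section 2.8.1 states that "randomisation will be on a cluster basis, the unit of randomisation being the defibrillator" and that "defibrillators shall be allocated to a treatment arm in a 1: 1: 1 ratio using simple randomisation". It adds that "Defibrillators are allocated to specific vehicles (ambulances or rapid response cars) and are not usually moved between vehicles", and that "defibrillator bags will be marked with the callsign of their allocated vehicle and display stickers reminding staff not to move them". A cluster was later clarified as a defibrillator carried by its associated vehicle. No rotation or re-randomisation is described.

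**Awareness of the arm.** Section 2.8.1 says: "At the point of device charging, staff will know which treatment they are delivering and so will not be blinded". Section 2.10.1 likewise ties it to seeing the energy on charging. The bias named in 2.8.1 is performance bias, to be assessed with variables such as conveyance by arm. Section 2.10.1 adds that control room staff do not know the arm and that the closest available ambulance is normally sent.

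**Entry.** Section 2.5: "A patient may be eligible, but not recruited, if the incident was attended by a POSED vehicle carrying its allocated defibrillator", where the shocks came from an ambulance-service device outside the study.

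**Primary result.** Section 6.2.3.2: "We will report the proportion of eligible patients who receive the randomised intervention". Section 2.3.1 gives the primary outcome as the numbers eligible and recruited. Neither mentions the arm.

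**Crew views.** In the scoping exercise (section 2.1), "70% of paramedics felt that the first shock should be >120J whilst 95% felt that an escalating regime should be used". The same paragraph reports that 95% were willing to take part and that 30% did not know their devices' programmed energies.

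**The concern.** Sections 2.8.1 and 2.10.1 treat awareness as arising at charging, when the patient is already being treated under the allocation. With one allocation per vehicle-bound device, that describes only its first use. Later crews can know the arm on the way to the patient.

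This matters because the choice of device at the scene decides whether a patient is recruited (section 2.5). It may also decide the arm, because nothing says where a patient belongs when two study vehicles attend. The safeguards in 2.10.1 protect dispatch, not that choice.

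Section 1.3 gives paramedic engagement and beliefs about randomised treatments as a reason for running the study. Of the three strategies in section 2.1, only Group 2 both starts above 120J and escalates, so a preference between arms is plausible. At stake is whether the study can say that allocation survives on scene, which a main trial would need to know.

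**Working it through.** **The plan's own figure.** Section 6.1 aims for 90 patients, ideally 30 per arm: 3 × 30 = 90. No power or precision calculation is given, and no number of eligible patients. The denominators and switch rates below are therefore assumptions.

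**1. One primary result, several patterns by arm.** Assume 120 eligible (40 per arm) and 90 recruited. The proportion is 90/120 = 75.0% (Wilson 95% CI 66.6% to 81.9%) in every row.

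| Pattern | Group 1 | Group 2 | Group 3 | Pooled |
|---|---|---|---|---|
| Loss unrelated to arm | 30/40 (75%) | 30/40 (75%) | 30/40 (75%) | 90/120 |
| More loss in Group 1 | 22/40 (55%) | 34/40 (85%) | 34/40 (85%) | 90/120 |
| Loss only in Groups 1 and 3 | 25/40 (62.5%) | 40/40 (100%) | 25/40 (62.5%) | 90/120 |

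With other denominators, 90 recruited gives 90% (of 100), 60% (of 150) or 50% (of 180). None carries information about the arm.

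**2. Switch to a device outside the study.** Assume 30 eligible patients per arm and a fraction s switched away in Groups 1 and 3. Pooled proportion = (30 + 60(1 − s))/90.

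- s = 0.1: 84/90 = 93%; by arm 90/100/90%
- s = 0.2: 78/90 = 87%; by arm 80/100/80%
- s = 0.3: 72/90 = 80%; by arm 70/100/70%

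The pooled figure does fall. What it cannot show is that the loss depends on the arm.

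**3. Switch to a Group 2 study device, counted under the device used.** Arm counts are 30(1− s), 30 + 60s and 30(1 − s), which always sum to 90.

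- s = 0.1: 27/36/27
- s = 0.2: 24/42/24
- s = 0.3: 21/48/21

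The pooled proportion stays at 90/90 = 100%.

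**4. Would unequal arm sizes give it away?** Only in part. Even if patients were allocated independently, the standard deviation of one arm's count would be √(90 × 1/3 × 2/3) = 4.5. A count of 36 is then 6/4.5 = 1.3 SD above 30, which is unremarkable; 42 is 12/4.5 = 2.7 SD above. Simple randomisation of devices that see different numbers of patients adds further spread, so an imbalance could not readily be attributed to switching.

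**5. Would adherence show it?** Sections 2.9.2 and 6.2.3.3 compare delivered with allocated energy. If the allocation is read from the device used, a patient moved between two study devices before the first shock counts as compliant. The protocol does not say how it is read.

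**The case against.** **What stands on the other side.** The study is openly unblinded, and section 2.8.1 justifies cluster allocation by the delay that individual randomisation would cause. Section 6.2.3 leaves summary and display to an analysis plan not seen here, and 6.2.3.2 does not rule out a split by arm. Section 6.2.3.1 plans baseline comparability on features set before or at entry, and a CONSORT flow diagram. Screening logs (2.5), device downloads (2.9.2) and focus groups (3.4) add more. After a change of device mid-episode, 2.8.1 applies normal trust policy, so only a choice made before the first shock could change the arm. These sources are partial: none is said to give eligible and recruited counts by allocated arm, and where to place a patient attended by two study vehicles is a matter of definition, not display.

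**Stronger readings that the protocol does not support.**

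- *Crews know every later patient's arm.* Nothing says that crews stay with one vehicle, and 30% did not know their devices' energies. Recruiting 90 patients over months 4 to 24 (section 7.6) is about 90/21 = 4.3 a month across all study vehicles. Crews can know; it is not shown that they do.
- *Steering took place.* There is no evidence of it. The preferences come from a small exercise in which 95% were willing to take part.
- *Conveyance is the only check.* Section 2.8.1 offers it as an example, and 6.2.3.1 adds others.
- *Crews might withhold a shock because of the arm.* Section 2.4.1 has shocks delivered under national guidelines, and nothing suggests otherwise.
- *Survival comparisons would be biased by a given amount.* The protocol gives no survival figure for switched patients, and section 6.2.1 disclaims formal analysis of differences.

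**Conclusion.** The point holds as a limited gap in design and reporting. One-off randomisation of vehicle-bound devices and unblinded use together mean that the arm can be known before attendance, which sections 2.8.1 and 2.10.1 do not acknowledge. Recruitment depends on the device used at the scene, and no rule fixes the arm when two study vehicles attend. The unsplit primary proportion then looks the same with and without arm-dependent loss: 75.0% in all three patterns above. It need not move at all when the switch is between study devices.

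These sizes rest on assumed denominators and switch rates. The conclusion that an unsplit figure cannot show dependence on the arm does not. The change should be made because it bears directly on whether a main trial is feasible and costs little.

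**What to change.** **Section 2.8.1.** State that the allocation may be known to crews before attendance. Define each patient's analysis arm as that of the first-arriving study vehicle carrying its allocated defibrillator, whichever device delivered the shock. This is a rule for analysis only and changes nothing in treatment.

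**Section 6.2.3.2.** Report by that arm, as well as pooled:

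- eligible, recruited and eligible-but-not-recruited counts, with the primary proportion;
- incidents attended by more than one study vehicle;
- patients shocked by a device other than that of the first-arriving study vehicle.

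**Cost.** Wording, plus one derived variable. Response times already come from call-centre databases (section 3.1.1), but section 5.4 requires only call details and an eligibility assessment for potential participants, so the vehicle callsign must be kept for eligible cases not recruited. The service tracks vehicles rather than defibrillators (2.8.1), so arrival times alone do not confirm that the device was aboard. Section 2.5 already uses that condition for these patients, so it has to be established anyway.

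Some patients will appear under an arm whose device did not treat them. Per-arm figures will be descriptive: at an assumed 40 per arm, power to separate 85% from 55% is about 85%, and 75% from 55% about 47%.
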